2.0 STUDY SYNOPSIS AND SCHEMA

Study Objectives

This study will evaluate the effects of a comprehensive diagnostic approach to enhance the percentage of participants that receive their HIV testing results and counseling, given they are HIV positive on the initial EIA screening. All enrolled participants will be followed for 12 months with the viral load (VL) measured at that time point in addition to the status of any HIV treatment they have received.

Study Design

The study consists of a cluster randomized trial (CRT) at county hospitals in Guangxi, China to assess the effectiveness of a structural intervention: a new testing algorithm, consisting of rapid point-of-care (POC) HIV and CD4 testing, with viral load (VL) testing in parallel, designed to ensure completeness of diagnostic assessment and accelerate time to ART initiation for patients deemed ART eligible (hereafter called the One4all Test Intervention).

This CRT will be conducted in 12 county general hospitals with an estimated average of 30 participants per hospital, totaling an estimated 360 participants. The unit of randomization is the hospital. Hospitals will be randomized to 1) theOne4all Test Intervention, or 2) the control condition, consisting of the current standard of care (SOC). The efficacy of the intervention will be evaluated at 1, 3 and 12-month follow-up assessments, and the differential efficacy for drug users (DUs) and non-drug users will be examined, if an adequate number of DUs is enrolled.

Study Population

The study population will consist of adult participants who screen positive on an initial HIV enzyme immunoassay (EIA) in the 12 study hospitals. Since the study will be conducted in China, the vast majority of participants will be of Chinese or Asian descent. Women will be included and are expected to represent approximately 26% of the study population.

Eliqibility Criteria

Site Eligibility Criteria: The location of our study is Guangxi Zhuang Autonomous Region (Guangxi). We will select county-level general hospitals in order to ensure sufficient caseload at each hospital and homogeneity across hospitals. Guangxi counties usually have one general hospital (a limited number of counties have two or more general hospitals); this hospital has been designated as the only setting for delivering ART services in the respective county.

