13.0 STATISTICAL ANALYSIS

13.1 General Design

13.1.1 Study Hypotheses

Hypothesis 1a

The new testing algorithm will increase the proportion of individuals who have completed all tests to confirm HIV diagnosis and received counseling within 30 days of screening HIV-positive, given they have screened HIV-positive on the initial EIA, from 23% to at least 50% (primary outcome).

Hypothesis 1b

The new testing algorithm will increase the proportion of individuals with a CD4 ≤350 cells/mm³ who initiate ART within 90 days of screening, given that they have screened HIV positive on the initial EIA (secondary outcome).

Hypothesis 1c

The effectiveness of the new testing algorithm will yield no significant differences for DUs at 1-month follow-up on testing completeness and at 3-month follow-up on ART treatment initiation, compared to non-DUs.

Hypothesis 2

The new testing algorithm will increase the proportion of individuals with a $VL \le 200$ copies/mL at 12 months, given that they have screened HIV positive on the initial EIA (tertiary outcome).

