Study participants will be classified as drug users or non-drug users based on the baseline assessment. A variable will be included in the statistical model for the primary and secondary outcomes to estimate the association between drug user status and receipt of post-test results and counseling following testing completeness and the initiation of ART therapy, respectively.

Tertiary Outcome (Hypothesis 2)

A tertiary outcome is the proportion of participants who have viral suppression based on the 12-month viral load test, where viral suppression is defined as viral load \leq 200 copies/mL. We will define the tertiary endpoint variable as a binary variable. If a participant with VL \leq 200 copies/mL at 12 months after initial screening, the variable is defined equal to one. Otherwise, the variable is defined equal to zero. All participants who screened HIV-positive on the initial EIA at screening will be included in the analysis.

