13.3 Statistical Methods for Primary and Secondary Outcomes

13.3.1 Primary Outcome

Primary Analysis for Hypothesis 1a

Hierarchical regression models (e.g., mixed-effect models or random-effect models (48, 49)) will be used to compare the proportion of HIV-positive individuals who received a complete suite of test services, results and post-test counseling within 30 days between individuals assigned to the One4all Test Intervention arm (i.e., individuals who receive a new testing algorithm, consisting of HIV, CD4, and VL tests) and individuals receiving SOC in the control arm. Specifically, proportions will be compared using logistic regression with hospital-level random effects to account for potential ICC within hospitals. Models that do not account for ICC will underestimate standard errors. Testing completeness rates will be compared at 30 days after being screened HIV-positive in the hospital. In addition to the inclusion of a covariate for the intervention arm (1=intervention, 0=SOC), random effect logistic regression models will control for the stratification factor and potential confounding variables, including age, gender, transmission mode, drug use, and other characteristics that are found to differ at baseline.

Secondary Analyses for Hypothesis 1a

A secondary analysis of primary endpoint will also be performed: comparison between the time from initial EIA positive screen to completion of testing between the two treatment groups, not

restricted to the 30 days period. Participants who did not complete testing will be censored at the endpoint of the study. Kaplan-Maier will be used to compare time differences by days from the positive HIV screening to the receipt of post-test counseling (can extend beyond the 30 day cut point period) between the intervention and control groups. An extended Cox model accounting for the effects of clustering will be used to calculate the intervention effect by hazard ratios while controlling for other covariates. Further, testing completeness will be compared between the two treatment groups at additional thresholds of 45, 60, and 90 days, analyzing these endpoints in a similar fashion to the primary analysis.

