The analyses described above (for Hypotheses 1a and 1b) will be repeated by including a predictor variable in the statistical model that is defined by classifying study participants as drug users or non-drug users based on the baseline assessment. This analysis will estimate the association between drug use status at baseline and testing completeness at 1-month follow-up and ART initiation at 3-month follow-up between the One4all Test Intervention and the SOC control groups.

Analysis for Hypothesis 2

The number of participants who have a $VL \le 200$ copies/mL at 12 months will be defined as the numerator for both the One4all Test Intervention and the SOC control groups, separately. The

denominator will be defined as the number of participants who had a HIV-positive initial EIA screening. Similar to analysis for Hypothesis 1a, random-effect logistic regression will be used to compare the proportion of participants virally suppressed between the two groups. Additional descriptive analyses will be performed related to this tertiary outcome, including describing the ART therapy regimen and the adherence to the regimen.

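### Hypothesis 1c asks whether the intervention works differently in drug users, but the specified model adds only a drug-user predictor and no arm-by-drug-use term

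*Protocol*

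**What the plan says.** Hypothesis 1c in Protocol 13.1.1 reads: "The effectiveness of the new testing algorithm will yield no significant differences for DUs at 1-month follow-up on testing completeness". It goes on to cover ART initiation at 3 months, with non-users as the comparison. The synopsis (2.0) describes the same aim conditionally: "the differential efficacy for drug users (DUs) and non-drug users will be examined, if an adequate number of DUs is enrolled". Section 4.1.1 also speaks of a differential impact on drug users, and 4.2 of differential effectiveness, with the caveat that cases may be too few.

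The analysis is described twice:

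- Section 13.1.2, which labels 1c a secondary outcome, includes a drug-user variable in the model "to estimate the association between drug user status and receipt of post-test results and counseling following testing completeness", and likewise for ART initiation.
- Section 13.3.2 says the 1a and 1b analyses "will be repeated by including a predictor variable in the statistical model that is defined by classifying study participants as drug users" or non-users. It then states the target: "This analysis will estimate the association between drug use status at baseline and testing completeness at 1-month follow-up". The same sentence adds ART initiation and closes with a reference to the two study arms.

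Neither section names an interaction term, an arm effect within drug users, an equivalence margin or an interval criterion. Section 13.3.1 already lists "potential confounding variables, including age, gender, transmission mode, drug use, and other characteristics that are found to differ at baseline" among the adjustments for 1a. Section 13.4 applies a 5% one-tailed test to the primary and secondary endpoints.

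**The concern.** A drug-user term without an interaction estimates whether drug users complete testing, or start ART, more or less often than non-users, averaged over the arms. Hypothesis 1c asks whether the difference between arms is the same in the two groups. These quantities can move independently. The drug-user coefficient can be near zero while the intervention fails in drug users, and clearly non-zero while the intervention works equally well in both groups.

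Two further features weaken 1c. It predicts the absence of a significant difference, so a small and imprecise subgroup favours it, and no margin says how large a difference would matter. And the one-tailed rule in 13.4 has no direction to apply to a no-difference hypothesis.

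At stake is the trial's only statement on drug users. Following the text would yield a number labelled as the answer to 1c that does not measure differential effectiveness.

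**Working it through.** **Inputs, all from the Protocol.** 180 participants per arm in 6 hospitals of 30; about 10% drug users; completeness 0.22 control and 0.50 intervention; ICC 0.082; ART initiation 0.14 and 0.40 (all 13.2). Drug users are 8% of newly identified and 12% of existing cases (4.1.1). So there are about 18 drug users and 162 non-users per arm, with a range of 14 (8% × 180 = 14.4) to 22 (12% × 180 = 21.6) drug users.

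**The plan's own figure.** Section 13.2 gives 93% power for the primary outcome (93.6% in its table) and none for 1c.

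- Design effect = 1 + 29 × 0.082 = 3.378; effective n = 180/3.378 = 53.3 per arm.
- Unpooled SE = √[(0.22×0.78 + 0.50×0.50)/53.3] = 0.089.
- 0.28/0.089 = 3.15; less 1.645 gives 1.50, so one-sided power is 93.4%. The stated figure is reproduced.

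**Does the drug-user coefficient track 1c?** Simulation: 1,500 trials per scenario, 12 hospitals of 30 with 3 drug users each, ICC 0.082 placed on the logit scale, logistic models with hospital indicators (which absorb arm), two-sided 5%. Non-users go from 22% to 50% throughout.

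| Drug users, control to intervention | Drug-user term significant | Median drug-user coefficient | Interaction significant |
|---|---|---|---|
| 22% to 50% (same effect, same rates) | 4.5% | −0.01 | 4.7% |
| 22% to 22% (no benefit) | 38% | −0.76 | 31% |
| 36% to 36% (no benefit) | 6% | 0.01 | 39% |
| 9.4% to 26.9% (same odds ratio, lower rates) | 60% | −1.02 | 2.6% |

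In the third row the intervention does nothing for drug users, yet the drug-user term is silent. In the fourth it works equally well on the odds-ratio scale, yet the term is usually significant.

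**What a correct interaction could show.** Wald test of the interaction log odds ratio, no design effect because the contrast is largely within hospital, 18 drug users per arm, same control rate in both groups.

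- *No benefit in drug users.* Effect = ln(0.50/0.50) − ln(0.22/0.78) = 1.27. SE = √[2/(18×0.1716) + 1/(162×0.1716) + 1/(162×0.25)] = 0.84. z = 1.50; two-sided power = Φ(1.50 − 1.96) ≈ 32%, or 44% one-sided. With 14 to 22 drug users per arm: 27% to 38% two-sided. The simulation gave 31%.
- *Half the log-odds effect in drug users* (22% to 34.7%). Effect 0.63, SE 0.79, power about 12%.
- *ART initiation, 0.14 to 0.40.* About 29% for no benefit and 12% for half the log-odds effect.
- *Truly equal effects.* SE = √[1/(18×0.1716) + 1/(18×0.25) + 1/(162×0.1716) + 1/(162×0.25)] = 0.78. The 95% interval for the ratio of odds ratios extends by a factor of exp(1.96 × 0.78) ≈ 4.6 either way (5.6 for ART).

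On the risk-difference scale the no-benefit case has SE = √[(0.1716+0.1716)/18 + (0.1716+0.25)/162] = 0.147, hence 0.28/0.147 = 1.90 and power of about 48%. The planned model is logistic, so 32% is the relevant figure: about 68% of such trials would show no significant difference.

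**The case against.** The best counter-argument is the end of the target sentence in 13.3.2, which refers to the two arms. An association of drug use with the outcome, compared between arms, could be loosely worded effect modification. But no model term delivers that comparison, and the parallel text in 13.1.2 has no such phrase. The ambiguity softens the charge without removing it.

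The unseen SAP might specify the interaction. Section 13.1.3, however, leaves to the SAP only how covariates are chosen. The protocol itself fixes a model and a target for 1c that do not match the hypothesis.

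Sections 2.0 and 4.2 already concede that drug users may be too few. This stands, and it answers part of the power argument. It does not answer the mismatch, since more drug users would not make a main effect measure differential effectiveness.

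A reader might infer two stronger points that the document does not support:

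- *That the repeated analysis adds nothing because drug use is already in the 1a model.* Section 13.1.3 describes the candidate covariate differently (injection versus non-injection, opiate versus non-opiate) and only as something to be considered, and 13.3.2 lists no covariates for 1b. The overlap is likely but not established.
- *That the trial will report equality by default.* No section says a non-significant result will be presented as equal effectiveness. Only the wording of 1c invites that reading, and the caveat in 4.2 points towards caution.

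**Conclusion.** The point holds. The analysis in 13.1.2 and 13.3.2 targets the association of drug use with the outcome, while 1c and sections 2.0, 4.1.1 and 4.2 pose a question about the intervention effect. Followed literally, the plan produces a coefficient that can mislead in either direction. Once the right term is fitted, about 36 drug users give roughly 32% power against a complete absence of benefit and 12% against half the log-odds effect, so a non-significant result would not support 1c.

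These figures assume about 10% drug users spread evenly over hospitals, the planning rates in 13.2, the same control rate in both groups for the power calculations, and no design effect on the within-hospital contrast.

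The flaw is confined to a secondary hypothesis that is conditional on enrolment and absent from the objectives in 5.1 and the outcome measures in 8.1. It should be fixed, but it does not touch the primary, ART or viral-load comparisons.

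**What to change.** - In 13.3.2, with matching text in 13.1.2, specify arm + drug user + arm × drug user with the hospital random effect, for both completeness and ART initiation.
- Report the arm effect in drug users and in non-users, and their contrast (the ratio of odds ratios) with a two-sided confidence interval. State that the one-tailed rule in 13.4 does not apply to 1c.
- Reword 1c in 13.1.1 as an exploratory estimate of that contrast, and say that a non-significant result will not be read as equal effectiveness.

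The cost is one model term and a few sentences. No new data are needed, because drug use is recorded at baseline (9.4 and 11.2.1). The downside is a visibly wide interval, which is an honest account of what about 18 drug users per arm can show. The change should be made before outcomes are analysed by arm.

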13.4 Significance Testing

A 5% level one-tailed test will be used for the analysis of the primary endpoint and secondary endpoints.

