13.1.2 Primary and Secondary Outcomes (Endpoints)

Primary Outcome (Hypothesis 1a)

The primary outcome of this study is the receipt of post-test results and counseling following testing completeness. The numerator is the number of HIV-positive participants who have received post-test results and counseling within 30 days of initial screening blood draw. The denominator is the number of participants who screened positive on the initial HIV EIA in the study arm (control or intervention).

Testing completeness is defined as completion of all three required components: 1) rapid, POC HIV testing, 2) CD4 testing, and 3) confirmatory testing by WB in the SOC or confirmatory testing by VL in the One4all.

The primary endpoint variable (receipt of all post-test results and counseling) will be defined as a binary variable. If an HIV-positive individual has completed and received results on the three required testing components (as defined above) and received post-test counseling within 30 days from his/her HIV screening, it is defined as a complete case, and the variable is defined equal to one. If any test, all three test results, or post-testing counseling are missing, we will define the case as an incomplete case, and the variable is defined equal to zero. Only individuals who have screened positive on the initial EIA will be analyzed. A secondary analysis of the primary endpoint will compare between the two treatment groups time from EIA screening to testing completeness among those who screened HIV-positive on the initial EIA but not restricting to the 30 days period, with those not completing testing censored at the endpoint of the study.

Secondary Outcome (Hypothesis 1b)

A secondary outcome is the proportion of treatment-eligible participants with CD4 \leq 350 cells/mm³ who have initiated ART within 90 days of an initial positive HIV screening. We will define the secondary endpoint variable for Hypothesis 1b as a binary variable. If a participant with CD4 \leq 350 cells/mm³ initiates ART within 90 days of a positive screening, the variable is defined equal to one. Otherwise, the variable is defined equal to zero. All participants who screened HIV-positive on the initial EIA at screening will be included in the analysis.

Secondary Outcome (Hypothesis 1c)

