13.2 Rationale for Sample Size and Statistical Power

We have selected a sample size of 180 HIV-positive participants (including approximately 10% DUs) in the control arm and 180 (including approximately 10% DUs) in the intervention arm, across 12 clusters (n=30 individuals in each cluster). This sample will achieve 93% power

based on a one-sided test (alpha=0.05) to detect a difference between the group proportions of 0.28, where under the alternative hypothesis the intervention group proportion is assumed to 0.50 and the control group proportion is assumed to be 0.22. This calculation assumes an intracluster correlation (ICC) within hospitals of 0.082 based on preliminary data. To assess the sensitivity of these calculations based on the 12 clusters and 30 patients per cluster, we examined in the table below effect sizes of 0.28, 0.33, and 0.38 and ICC estimates of 0.072, 0.082, and 0.092, assuming a one-side test at alpha=0.05 and the SOC success rate of 0.22.

		Intra-cluster correlation (ICC)		
		0.072	0.082	0.092
Success rate in One4All	0.50 (delta=0.28)	95.2%	93.6%	92.0%
	0.55 (delta=0.33)	98.8%	98.2%	97.5%
	0.60 (delta=0.38)	99.8%	99.7%	99.5%

Power calculations were also performed for the secondary outcome of initiating ART within 90 days and having a CD4 count \leq 350, among all the HIV-screened positive study participants. Data from preliminary data in Guangxi showed that 14% of HIV screened positive patients had CD4 counts \leq 350 and initiated ART within 90 days. We will have 93% power to detect an increase to 40% in the intervention group of initiating ART with CD4 \leq 350 within 90 days. For these calculations, we used an ICC of 0.082 and a one-sided test at alpha=0.05. All power calculations were performed by the PASS (Version 8) software.

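### The one-tailed rule in Protocol section 13.4, read as written, reaches Hypothesis 1c, which has no direction; limit it to the directional between-arm tests

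*Protocol*

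**What the plan says.** Section 13.4 is a single sentence: "A 5% level one-tailed test will be used for the analysis of the primary endpoint and secondary endpoints". It makes no exception and names no tail.

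Section 13.1.1 gives the hypotheses. 1a and 1b are directional. For example, 1b reads "The new testing algorithm will increase the proportion of individuals with a CD4 ≤350 cells/mm³ who initiate ART within 90 days of screening". Hypothesis 1c is different in kind: "The effectiveness of the new testing algorithm will yield no significant differences for DUs at 1-month follow-up on testing completeness", with the same statement for ART initiation at 3 months, in comparison with non-users.

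Section 13.1.2, whose title covers primary and secondary outcomes and equates them with endpoints, introduces 1c under a sub-heading that begins "Secondary Outcome (Hypothesis 1c". The analysis of 1c sits in section 13.3.2, Secondary Outcomes. It repeats the 1a and 1b models with a drug-user variable added: "This analysis will estimate the association between drug use status at baseline and testing completeness at 1-month follow-up and ART initiation at 3-month follow-up". Neither section gives 1c a tail, a sidedness or a margin of its own.

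The power calculation in section 13.2 is also one-sided: "based on a one-sided test (alpha=0.05) to detect a difference between the group proportions of 0.28". It concerns 1a, with a parallel calculation for 1b. No power is stated for 1c.

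**The concern.** A one-tailed test suits a hypothesis that predicts a direction. Hypotheses 1a and 1b do; 1c does not. Applying the blanket rule to 1c has two consequences.

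First, one direction of difference is left practically undetectable, and the protocol does not say which. Both directions are conceivable. Section 4.1.1 describes drug users as facing particular difficulties at each step of care and as often lost straight after testing, so they might gain less from the new algorithm. An algorithm with fewer early steps might also help them more.

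Second, 1c is worded so that a non-significant result agrees with it. A real difference in the untested tail would therefore not only be missed; it would be counted as support for equal effectiveness in drug users, a group whose differential response the protocol sets out to examine. If the tail were instead chosen after seeing the data, the true two-sided error rate would be 2 × 5% = 10%.

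**Working it through.** **1. Does the one-sided rule match the plan's own power figures?**

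Inputs from section 13.2: 180 per arm, 12 hospitals of 30, one-sided alpha 0.05. On the rates, "the intervention group proportion is assumed to 0.50 and the control group proportion is assumed to be 0.22". On clustering, "This calculation assumes an intracluster correlation (ICC) within hospitals of 0.082 based on preliminary data".

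- Design effect = 1 + (30 − 1) × 0.082 = 3.378.
- Effective n per arm = 180 / 3.378 = 53.3.
- Unpooled SE = √[(0.22 × 0.78 + 0.50 × 0.50) / 53.3] = 0.0889.
- One-sided power = Φ(0.28 / 0.0889 − 1.645) = 93.4%. The pooled variant gives 92.3%.
- The protocol states 93% in the text and 93.6% in the table. Unpooled values for all nine table cells fall within 0.4 percentage points of those printed.
- For 1b (14% against 40%), one-sided power is 92.5% (pooled) to 93.5% (unpooled), against 93% stated.
- Two-sided versions give 86.4% to 88.3% for 1a and 86.7% to 88.5% for 1b, which do not match the stated figures.

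So the one-sided test was planned for 1a and 1b, consistently with their wording. These figures stay as they are if only 1c is made two-sided.

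**2. What a one-sided test does to a difference in the other tail**

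With a normally distributed estimate, the chance of rejection when the true effect lies opposite to the tested tail is

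P = Φ(−1.645 − |effect| / SE).

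This is 5% at zero effect, below 5% at any non-zero effect, and tends to 0 as the effect grows. It holds whatever model term is tested.

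**3. Illustration: drug-user-by-arm difference**

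The protocol expects about 10% drug users, so 0.10 × 180 = 18 per arm, with 162 non-users. Assumptions not in the protocol: rates of 0.22 and 0.50 apply within both subgroups for the variance, and clustering is ignored.

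- Variance = 0.1716/18 + 0.25/18 + 0.1716/162 + 0.25/162 = 0.02602, so SE = 0.161.
- For a difference of 0.20: tested tail Φ(0.20/0.161 − 1.645); two-sided Φ(0.20/0.161 − 1.960); other tail Φ(−0.20/0.161 − 1.645).

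| True difference | One-sided, tested tail | Two-sided | One-sided, other tail |
|---|---|---|---|
| 0.10 | 15.3% | 9.0% | 1.2% |
| 0.20 | 34.3% | 23.6% | 0.2% |
| 0.28 | 53.6% | 41.1% | 0.04% |

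**4. Illustration: drug-user main effect**

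Sections 13.1.2 and 13.3.2 describe adding a drug-user variable, so the term may be a main effect. Take 36 users and 324 non-users, a rate of (0.22 + 0.50)/2 = 0.36 in non-users and 0.16 in users, again ignoring clustering.

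- Pooled rate = (324 × 0.36 + 36 × 0.16)/360 = 0.34.
- Null SE = √[0.34 × 0.66 × (1/324 + 1/36)] = 0.0832.
- SE under the alternative = √(0.36 × 0.64/324 + 0.16 × 0.84/36) = 0.0667.
- Tested tail: Φ[(0.20 − 1.645 × 0.0832)/0.0667] = 82.8%.
- Two-sided: 71.0%.
- Other tail: Φ[(−0.20 − 1.645 × 0.0832)/0.0667] = Φ(−5.05), effectively nil.

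Here a difference that a two-sided test would usually detect is lost if it falls in the untested tail.

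**The case against.** The strongest reply is that 13.4 was never meant for 1c. The synopsis (Outcome Assessments) and sections 5.1.2 and 8.1.2 name only ART initiation as the secondary objective or outcome. In 13.1.2 a secondary endpoint variable is defined for 1b, and none is defined for 1c. The 1c text there adds a drug-user variable to the models for the primary and secondary outcomes, which it identifies as receipt of results with counseling and ART initiation. On that reading the secondary endpoints in 13.4 are those of 1b, and the rule governs arm comparisons only. Sections 13.1.2 and 13.3.2 also describe the 1c analysis as estimating an association, and an estimate shows a gap in either direction.

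Much of this stands: coverage of 1c depends on the label in 13.1.2 and the placement in 13.3.2. It does not remove the point. Those two sections belong to the same statistical chapter as 13.4, nothing exempts 1c, and 1c is itself phrased in terms of significance, so a test is implied.

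Two stronger readings should be resisted. A reader might infer that the plan definitely makes a gap to the disadvantage of drug users impossible to declare. The documents do not support that: no tail is named, and if the tail were drug users doing worse, a one-sided test would be more sensitive to that gap (34% against 24% in the first illustration). A reader might also blame sidedness for a likely false finding of no difference with only 18 drug users per arm. That is a power problem, which a two-sided test does not cure. The protocol partly concedes it: section 4.2 allows that there may be too few cases, and the synopsis makes the comparison conditional on adequate numbers.

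**Conclusion.** The point holds in a limited form. As written, section 13.4 together with the classification in 13.1.2 assigns a one-tailed test to a hypothesis without direction, and does so without naming the tail. A true difference in the opposite tail would be declared with probability below 5% (0.2% in the interaction example at 0.20), and the resulting non-significance would agree with the hypothesis. This rests on reading the secondary label literally; the competing reading, that 13.4 covers only 1a and 1b, is plausible, and the text should settle it.

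The example figures rest on assumed subgroup rates and ignore clustering. The bound of 5% needs only a valid one-sided 5% test with an approximately normal statistic. The impact is confined to 1c. The one-sided rule fits the wording of 1a and 1b, and their stated power is reproduced and unaffected.

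**What to change.** Reword section 13.4 so that the one-tailed 5% test applies to the between-arm comparisons of Hypotheses 1a and 1b. State whether it also covers Hypothesis 2, which is directional but tertiary and so is not named in 13.4 at present.

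For 1c, specify a two-sided test and report the drug-user-related estimate with a two-sided 95% confidence interval. Add that a non-significant result will not be read as showing no difference. With few drug users expected, the interval is what shows how large a difference remains possible. A claim of similarity would need a pre-stated margin, which the protocol does not give.

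The cost is a sentence or two of text. Sample size, models, data collection and the stated power for 1a and 1b do not change.
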